12.2.11 PUSH(Pressure Ulcer Scale for Healing)

From Visit 2 (1d), the PUSH score will be checked at a 2-week interval (15d, 29d, 43d, 57d, 71d, 85d). Using a Version 3.0 PUSH tool, the score will be calculated according to the following criteria, and each sub-score and the total score will be recorded in the Case Report Form.

DIRECTIONS:

Observe and measure the pressure ulcer. Categorize the ulcer with respect to surface area, exudate, and type of wound tissue. Record a sub-score for each of these ulcer characteristics. Add the sub-scores to obtain the total score. A comparison of

Length	0 0 cm ²	1 <0.3 cm ²	2 0.3-0.6 cm ²	3 0.7-1.0 cm ²	4 1.1-2.0 cm ²	5 2.1-3.0 cm ²	
× Width	-	6 3.1-4.0 cm ²	7 4.1-8.0 cm ²	8 8.1-12.0 cm ²	9 12.1-24.0 cm ²	10 >24.0 cm ²	Sub-score
Exudate Amount	0 None	1 Light	2 Moderate	3 Heavy	-	-	Sub-score
Tissue Type	0 Closed	1 Epithelial Tissue	2 Granulation Tissue	3 Slough	4 Necrotic Tissue	-	Sub-score
-	-	-	-	-	-	-	Total Score

total scores measured over time provides an indication of the improvement or deterioration in pressure ulcer healing.

Length × Width: Measure the greatest length (head to toe) and the greatest width (side to side) using a centimeter ruler. Multiply these two measurements (length x width) to obtain an estimate of surface area in square centimeters (cm²). Caveat: Do not guess! Always use a centimeter ruler and always use the same method each time the ulcer is measured.

Exudate Amount: Estimate the amount of exudate (drainage) present after removal of the dressing and before applying any topical agent to the ulcer. Estimate the exudate (drainage) as none, light, moderate, or heavy.

Tissue Type: This refers to the types of tissue that are present in the wound (ulcer) bed. Score as a "4" if there is any necrotic tissue present. Score as a "3" if there is any amount of slough present and necrotic tissue is absent. Score as a "2" if the wound is clean and contains granulation tissue. A superficial wound that is reepithelializing is scored as a "1." When the wound is closed, score as a "0."

- 4 - Necrotic Tissue (Eschar):** black, brown, or tan tissue that adheres firmly to the wound bed or ulcer edges and may be either firmer or softer than surrounding skin.
- 3 - Slough:** yellow or white tissue that adheres to the ulcer bed in strings or thick clumps, or is mucinous.
- 2 - Granulation Tissue:** pink or beefy red tissue with a shiny, moist, granular appearance.
- 1 - Epithelial Tissue:** for superficial ulcers, new pink or shiny tissue (skin) that grows in from the edges or as islands on the ulcer surface.
- 0 - Closed/Resurfaced:** the wound is completely covered with epithelium (new skin).

[Reference: 1. PUSH Tool @ national Pressure Ulcer Advisory Panel

2. A Prospective Study of the Pressure Ulcer Scale for Healing (PUSH), Journal of Gerontology: MEDICAL SCIENCES 2005, Vol. 60A, No. 1, 93-97]

12.2.12 Subject diary

At every visit from Visit 2 (1d), a subject diary will be dispensed to record the frequency of self-dressing and the frequency of position changes per day.

13. Predicted precautions for use

13.1 Betafoam®

A. Contraindications

- (1) Hypersensitivity to povidone iodine included in this product
- (2) In case of rash, pyrexia, allergic reactions or infection symptoms developing while using this product, use of this product is prohibited and appropriate treatment should be instituted as instructed by the physician or pharmacist.
- (3) Thyroid dysfunction (in particular, nodular goiter, endemic goiter, Hashimotos thyroiditis), renal failure, newborns and infants less than 6 months old, herpeticum dermatitis, and before and after radioactive iodine treatment

B. Side effects

Dyspnea, flushing, hives, itching, rash, burning sensation, electrolyte and serum osmotic disorder, temporary renal failure, transient increase in serum protein-bound iodine, pulmonary edema

C. Warning or precautions

- (1) As this product is sterilized, it should be used immediately after opening the package, taking care to avoid contamination of the wound-contacting side.
- (2) This product should be used after consulting a physician or pharmacist.
- (3) In case of development of pruritus (flushing, inflammation), burning sensation, rash, or allergic reactions, consult a specialist.
- (4) Do not use the product if the sterilized pack is already opened or broken.
- (5) In case of severe bleeding, use the product after hemostasis.
- (6) On an infected wound (wound with symptoms such as flare, swelling, pain, feeling hot, strong malodor and pus discharge), use this product after eliminating the cause of bacterial proliferation such as a foreign substance, pus, or necrotized tissue.
- (7) As this product is for single-use only, re-use is prohibited.
- (8) In case of using this product immediately before delivery, wash the eyes of a newborn and bathe him/her as soon as possible after birth.
- (9) In case of using the product in broad burn patients, sufficient hydration should be implemented.
- (10) As this product may influence scintigraphy-based thyroid diagnosis, use of this product and scintigraphy should be separated by 1~2 weeks.

(11) In case of long-term, continuous use of this product, attention should be paid to thyroid dysfunction.

(12) Due to a possibility of a shock (anaphylaxis) in rare cases, in case of sudden development of itching, edema, heartburn, concurrently with severe facial pallor, cold extremities, cold sweat, or shortness of breath after using this product, immediately seek medical attention.

(13) Routine, long-term or broad use of this product is prohibited in pregnant women or women of childbearing potential or breastfeeding women.

(14) Concurrent use of this product with lithium, chlorhexidine, silver sulfadiazine compound, alkali, or mercury-containing agents may result in decreased antiseptic effects and discoloration. In addition, this product should not be used in combination with hydrogen peroxide.

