6.4 Packaging and labeling of investigational devices

Investigational devices will be labeled according to the Enforcement Regulations of the Medical Device Act (enforcement date 2015.07.29), Article 43, Attachment, and the label should include the following contents.

<Contents of the label>

1. "For a clinical study"
2. Brand name and model number
3. Lot No. and manufacturing date (can be substituted with an expiry date)
4. Storage conditions
5. Company name of the manufacturer or importer (including names of a manufacturer and a country, in case of commissioned manufacturing or import)
6. "Cannot be used for purposes other than a clinical study"
7. Subject number (if necessary)

7. Study subject

Pressure ulcer patients of the NPUAP Stage III

8. Subject Inclusion and exclusion criteria

This study will involve subjects who meet all of the following inclusion criteria and none of the exclusion criteria.

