8.1 Inclusion criteria

- 1) Adults aged at least 19 years old as of the consent date
- 2) Pressure ulcer of the NPUAP (National Pressure Ulcer Advisory Panel) Stage III at screening
- 3) Pressure ulcer size of 3-100 cm² at screening
- 4) Written consent provided by the subject or representative
(In case a subject has more than one pressure ulcers that meet all inclusion criteria, the largest one is selected as a target lesion.)

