8.2 Exclusion criteria

- 1) Any study ulcer of the NPUAP Stage I, II or IV
- 2) Diabetic ulcer or Venous ulcer (or stasis ulcer)
- 3) Past history of surgical treatment within 1 year or irradiation at the target pressure ulcer within 1 year
- 4) Hypersensitivity reaction to this product or povidone-iodine
- 5) Hyperthyroidism or thyroid disorder requiring drug treatment
- 6) Signs of a current underlying systemic infection (sepsis/bacterial infection/tuberculosis) or cellulitis or osteomyelitis
- 7) Type 1 diabetes
- 8) Current malnutrition
- 9) Heavy smoker: Current smoking level of ≥ 1 pack (20 cigarettes)/day of tobacco
- 10) Drug or alcohol addiction
- 11) Requirement of immunosuppressants during the study or current chemotherapy or radiotherapy
- 12) Application of other investigational product/medical device within 1 month prior to the

investigational device application (1d)

13) Pregnant or breastfeeding women

14) Other renal, hepatic, neurological, immunological disorder that may interfere with the wound healing process, at the discretion of the investigator

9. Target number of subjects and the rationale

The target number of subject enrollment is 20 subjects, with 10 subjects per group.

This study has a purely explorative goal so that no formal sample size calculation will be conducted but it was planned to enroll 10 subjects per group as the minimum sample size to achieve study objectives from a scientific perspective.

- ✓ Medifoam group: 10 subjects
- ✓ Betafoam group: 10 subjects

Even if a subject is withdrawn from the study, the subject will not be replaced.

10. Study method

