13.2 Medifoam®

A. Contraindications

In case of rash, pyrexia, allergic reactions or infection symptoms while using this product, use of this product is prohibited and appropriate treatment should be instituted as instructed by a physician.

B. Precautions and warnings

(1) As the status of exudate absorption can be observed from the back side of this product, exchange a dressing when the exudate has been absorbed or expanded to about 90% of the margin.

(2) In case of severe bleeding, use the product after hemostasis.

(3) On an infected wound (wound with symptoms such as flare, swelling, pain, feeling hot, strong malodor and pus discharge), use this product after eliminating the cause of bacterial proliferation such as a foreign substance, pus, or necrotized tissue.

(4) As this product is for single-use only, re-use is prohibited.

14. Discontinuation/withdrawal criteria and early completion criteria

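### The exclusion criteria in Protocol 8.2 are narrower than Betafoam's contraindications in 13.1 A(3), so a patient contraindicated for Betafoam can be eligible and be randomised to it

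*Protocol*

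**What the plan says.** Protocol 13.1 A(3) lists conditions in which Betafoam, the foam containing povidone-iodine, is contraindicated. The list opens with "Thyroid dysfunction (in particular, nodular goiter, endemic goiter, Hashimotos thyroiditis), renal failure", goes on to newborns and young infants, and ends with "herpeticum dermatitis, and before and after radioactive iodine treatment". Under side effects, 13.1 B includes "temporary renal failure, transient increase in serum protein-bound iodine, pulmonary edema". Under precautions, 13.1 C(11) adds: "In case of long-term, continuous use of this product, attention should be paid to thyroid dysfunction".

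The Medifoam contraindication in 13.2 concerns only reactions during use: "In case of rash, pyrexia, allergic reactions or infection symptoms while using this product, use of this product is prohibited". It has no thyroid, renal or iodine item.

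Eligibility is set by Protocol Section 8: "This study will involve subjects who meet all of the following inclusion criteria and none of the exclusion criteria". On the thyroid, 8.2 item 5 reads "Hyperthyroidism or thyroid disorder requiring drug treatment". Item 14 covers renal, hepatic, neurological and immunological disorders, but only where the investigator thinks that they could interfere with wound healing. Item 11 covers current radiotherapy. Item 3 covers irradiation of the target ulcer within the past year. The synopsis and SAP Section 4 repeat the same exclusion list.

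**The concern.** The protocol holds two lists that ought to agree, and they do not. A patient can satisfy every criterion in Section 8 and still have a condition in which the protocol says that one of the two study devices must not be used. Allocation is random, so eligibility for the study has to mean eligibility for either device.

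What is at stake is chiefly patient safety. The side effects and the long-term precaution in 13.1 show that the thyroid and renal items concern iodine exposure. Treatment lasts up to 12 weeks, on ulcers of up to 100 cm². Section 21.13 expects some subjects with limited communication or cognition, which makes an explicit written criterion more useful than reliance on what emerges at interview.

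**Working it through.** No arithmetic applies. The check sets each item of 13.1 A(3) beside the nearest criterion in 8.1 or 8.2 and asks who would still be eligible.

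| Item in 13.1 A(3) | Nearest criterion | Who still passes |
|---|---|---|
| Newborns and young infants | 8.1 item 1: "Adults aged at least 19 years old as of the consent date" | Nobody |
| Thyroid dysfunction; nodular goiter, endemic goiter and Hashimoto's named | 8.2 item 5 | A patient with one of these who is not hyperthyroid and needs no drug treatment |
| Renal failure, unqualified | 8.2 item 14 | A patient whose renal failure the investigator does not judge likely to interfere with wound healing |
| Radioactive iodine, before and after | Not named. Item 11 reaches at most current radiotherapy; item 3 only irradiation of the target ulcer | A patient with planned treatment, or with recent past treatment |
| Herpeticum dermatitis | Not named. At most item 14, if judged an immunological disorder that impairs healing | A patient not excluded by that discretionary route |

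The thyroid row is the clearest. A(3) carries no drug-treatment qualifier, item 5 does, and A(3) names conditions that can exist without hyperthyroidism and without drugs.

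The remaining steps on the way to the device do not close the gap:

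1. Screening (12.1.1, 12.2.2) measures TSH and creatinine, but no eligibility limit is attached to either. A euthyroid goiter would not show on TSH in any case.
2. Visit 2 (12.1.2, step 2) reviews the inclusion and exclusion criteria and randomises those found eligible. It does not call for a check against Section 13.
3. Section 10.3 applies the device according to the assigned group, again with no contraindication check described.
4. Section 14.1 does not name thyroid dysfunction or renal failure. Criterion 6 lets the investigator stop the device, at discretion and after application has begun.

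Section 8.2 already acts as the gate for Betafoam's contraindications in other respects. Item 4 carries over povidone-iodine hypersensitivity, which is 13.1 A(1), for both arms, and item 5 carries over part of the thyroid item. The protocol gives no reason for leaving out the rest.

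**The case against.** The strongest reply is that Section 13 is part of the protocol and investigators are bound by it. Section 22 requires them to know and implement the protocol, 21.5 asks for a thorough eligibility assessment by interview and tests, 21.9 allows the devices to be used only on an investigator's prescription, and 12.2.2 has laboratory results assessed for abnormality and clinical significance. This stands to the extent that it makes unnoticed use less likely. A reader might infer from the gap that contraindicated patients will receive Betafoam as a matter of course, and the documents do not support that. But these provisions are general or discretionary. They leave the protocol saying that the same patient is eligible under Section 8 and contraindicated under Section 13.

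On renal failure, item 14 names renal disorder and asks only that it might interfere with healing, which is a low threshold. So it would be wrong to read 8.2 as admitting renal failure generally. What remains is that the exclusion is discretionary and rests on a different question from the one that A(3) raises.

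Three further inferences are tempting and should not be drawn:

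- *A risk figure.* Equal allocation gives any one enrolled patient an even chance of Betafoam, but that only restates the design. The documents do not say how many such patients would be screened.
- *A score of how many A(3) items are covered.* Whether radioactive iodine counts as partly covered or simply not named depends on how item 11 is read, so a tally would reflect judgement.
- *A demonstrated bias between arms.* If the conflict came to light only after open-label allocation, the patient would be lost from Betafoam alone, because 13.2 has no matching item, and would not be replaced (Section 9). That requires a chain of events, and for any one patient never being given the device is an alternative to being exposed to it, so the two harms do not add. It is a side note.

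**Conclusion.** The point holds as a mismatch between two lists in the same protocol. Untreated, non-hyperthyroid nodular or endemic goiter or Hashimoto's thyroiditis is contraindicated for Betafoam and eligible for the study. Renal failure is left to discretion on a wound-healing test. Herpeticum dermatitis and radioactive iodine treatment are not named. Confidence in this reading is high, because it needs only the protocol's own text and no outside fact.

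The size of the consequence is unknown: no prevalence, expected number of patients or event risk can be derived. The conclusion assumes that Section 8 works as written, as the eligibility gate, and that the list in 13.1 A(3) is meant to apply to study subjects. It should be fixed, because it concerns safety and the correction is short.

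**What to change.** Amend 8.2 for both arms, with the check made before randomisation:

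- Item 5 becomes: *Hyperthyroidism or any thyroid dysfunction, treated or not, including nodular goiter, endemic goiter and Hashimoto's thyroiditis.*
- Add: *Renal failure, irrespective of its expected effect on wound healing*, with a limit on the screening creatinine set by the sponsor's clinicians.
- Add: *Herpeticum dermatitis.*
- Add: *Radioactive iodine treatment planned during the study, or received within a window before screening*, the window to be set by the sponsor's clinicians. Without a window the item would exclude any lifetime history, which is more than is needed.

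Applying the criteria to both arms keeps the groups comparable. It also fits 10.4, which allows povidone-iodine where necessary without limiting it to one arm.

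Use the TSH, creatinine and medical history already collected at screening. History is needed alongside TSH because a euthyroid goiter can have a normal TSH. The history items in 12.2.1 do not name radioactive iodine or herpeticum dermatitis, so sites should be told to ask about both. Repeat the new text in the synopsis and SAP Section 4.

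The cost is a short amendment, which needs IRB approval (21.2), two clinical limits to be decided, and possibly a few more screen failures, a number that the documents do not allow one to estimate. No new test is required.

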Pressure ulcer assessment ⁶ (digital photograph taking, investigator's photo evaluation) - Ulcer size (Using a scale) - Complete healing status	V ⁷	V	V	V	V	V	V	V	V	V	V	V	V	V	V	V	V	V	V	V	V	V	V	V	V	V

Item	Schedule	Screening		Treatment period																		Closing					
		1*	2*	3	4	5	6	7	8	9	10	11	12	13	14**												
		-14d~0d	1d (±1d)	5d* (±1d)	8d (±1d)	12d* (±1d)	15d (±1d)	19d* (±1d)	22d (±1d)	26d* (±1d)	29d (±1d)	33d* (±1d)	36d (±1d)	40d* (±1d)	43d (±1d)	47d* (±1d)	50d (±1d)	54d* (±1d)	57d (±1d)	61d* (±1d)	64d (±1d)	68d* (±1d)	71d (±1d)	75d* (±1d)	78d (±1d)	82d* (±2d)	85d (±2d)
PUSH		V			V				V				V				V			V							V
Self-dressing training		V		V	V	V	V	V	V	V	V	V	V	V	V	V	V	V	V	V	V	V	V	V	V	V	V
Dressing change frequency review				V	V	V	V	V	V	V	V	V	V	V	V	V	V	V	V	V	V	V	V	V	V	V	V
Infection sign checklist ⁸ (CSSC)		V		V	V	V	V	V	V	V	V	V	V	V	V	V	V	V	V	V	V	V	V	V	V	V	V
Subject diary distribution ⁹		V		V	V	V	V	V	V	V	V	V	V	V	V	V	V	V	V	V	V	V	V	V	V	V	V
Subject diary return				V	V	V	V	V	V	V	V	V	V	V	V	V	V	V	V	V	V	V	V	V	V	V	V
Concomitant medication/treatment review	V	V		V	V	V	V	V	V	V	V	V	V	V	V	V	V	V	V	V	V	V	V	V	V	V	V
Adverse event review		V		V	V	V	V	V	V	V	V	V	V	V	V	V	V	V	V	V	V	V	V	V	V	V	V

* Visit 1 and Visit 2 can take place on the same day.

** Subjects who have complete healing during the study or are withdrawn from the study will have all tests scheduled for V14.

¥ Subject do not make a site visit but perform self-dressing.

† Except for Randomization visit, Home Health Care system through study coordinator will be used for those subjects who aren't able to make a visit during the treatment period. Physical examination and measuring weight may be exempt in case of replacing visit with Home Health Care.

- Blood pressure, pulse, body temperature measurement
- Laboratory tests: If test findings within 2 weeks prior to the consent date are available, they may be used instead of screening findings.
 - Hematology: WBC, RBC, platelet, WBC count, Hb, Hct
 - Blood chemistry: AST, ALT, ALP, creatinine, BUN, total bilirubin, glucose, protein, albumin, gamma GTP, TSH (TSH is conducted at screening only)
- Urine hCG pregnancy test is conducted only in women of child-bearing potential.
- The investigational device is changed twice weekly; additional changes are allowed depending on the pressure ulcer condition, without any limitation to frequency.

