12.1.5 Unscheduled visit

In case it is necessary to conduct an unexpected and unscheduled visit due to reasons such as an adverse event, identify the purpose of the visit, review vital signs, adverse events and concomitant medication, and conduct laboratory tests, if necessary. There is no formal limitation in tests to be conducted during an unscheduled visit.

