12.2.2 Laboratory tests, urine hCG test

Laboratory test and urine hCF test will be conducted once at screening and at study completion/early completion.

- Sample collection and documentation: Blood samples are collected from subjects according to the test schedule using an aseptic technique, and collected blood samples are analyzed in a QC-certified clinical pathology lab using commercialized hematology, blood chemistry test methods. Test findings are recorded in the Case Report Form and assessed for normal/abnormal status or clinical significance, and for clinically significant abnormal findings, the investigator's opinion will be recorded.
- Test parameters:
 - ① Hematology: WBC, RBC, WBC Differential count, hemoglobin, hematocrit, platelets
 - ② Blood chemistry: AST, ALT, ALP, creatinine, BUN, total bilirubin, glucose, protein, albumin, gamma GTP, TSH (TSH is conducted at screening only.)
 - ③ Urine hCG test (to be conducted in all women, except for those who have been menopausal for at least 1 year or had hysterectomy, bilateral oophorectomy, or bilateral salpingectomy)

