17.1 Assessment method

An adverse event (AE) is any unintended sign (including abnormal laboratory finding), symptom, or disease occurring in a subject during the study, and does not necessarily have a causal relationship with the relevant investigational device.

An adverse device effect(ADE) is any untoward and unintended reaction caused by an investigational

device for which a causal relationship with the investigational device cannot be ruled out.

It is the responsibility of the principal investigator and sub-investigators to record all adverse events occurring during the study. Adverse events are to be recorded according to the MedDRA (Medical Dictionary for Regulatory Activities) and in case it is not possible, terms on signs and symptoms observed by the principal investigator or sub-investigators or spontaneously reported by a subject are to be recorded using medical terms.

In the Case Report Form, signs and symptoms of the adverse event, duration (onset and resolution dates), severity, causal relationship with the study device, action taken for the adverse event, and outcome should be recorded without omission.

The followings will be evaluated for safety assessment.

1) Adverse event

At every visit, review both local adverse events at the target pressure ulcer and other adverse events.

(Local adverse events at the target pressure ulcer: Erythema, edema, itching, flare, rash, others)

2) Vital signs

Vital signs are analyzed by measuring at every visit until study completion. Measured vital signs are blood pressure (in sitting), pulse, and body temperature. In addition, body weight is measured at screening, Week 4, and at the End-of-Study visit.

3) Laboratory tests and physical examination

Laboratory tests are conducted at screening and study completion. For physical examination, normal/abnormal status of findings at screening is confirmed, and it is assessed whether the subject is eligible for study participation.

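### Electrolyte and osmolality disturbance is a named Betafoam side effect, but no scheduled laboratory test measures it, so silent cases would not be found systematically or compared between arms

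*Protocol*

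**What the plan says.** Protocol section 13.1, in its list of Betafoam side effects, includes "electrolyte and serum osmotic disorder, temporary renal failure, transient increase in serum protein-bound iodine". Section 13.2, on Medifoam, gives contraindications and precautions but no side-effect list.

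The laboratory panel is set out in protocol section 12.2.2: "Hematology: WBC, RBC, WBC Differential count, hemoglobin, hematocrit, platelets" and "Blood chemistry: AST, ALT, ALP, creatinine, BUN, total bilirubin, glucose, protein, albumin, gamma GTP, TSH", with TSH at screening only. Footnote 2 of the Schedule of study activities gives the same chemistry list. Protocol section 17.1 fixes the timing: "Laboratory tests are conducted at screening and study completion". SAP section 7.2 says the same.

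The baseline sample need not be new. Footnote 2 of the schedule states: "If test findings within 2 weeks prior to the consent date are available, they may be used instead of screening findings".

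Outside the schedule, protocol section 12.1.5 tells the investigator at an unscheduled visit to "review vital signs, adverse events and concomitant medication, and conduct laboratory tests, if necessary", and it does not restrict which tests may be done. Section 17.1 counts an abnormal laboratory finding as an adverse event, and adverse events are reviewed at every visit.

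**The concern.** Safety is part of the stated aim in protocol section 5.2 and SAP section 2, and section 5.1 says that a further trial will build on this one. A randomised pilot adds to routine use a measurement made in the same way, at the same times, in both arms. For a side effect listed for one arm only, the plan makes no such measurement.

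Laboratory Tables 1003 and 1004 could therefore show nothing remarkable in either arm and still carry no information about electrolytes or osmolality. Someone planning the next trial could take that silence as reassurance. The routes that remain depend on something prompting a test. Protocol section 21.13 expects subjects with limited communication or cognition, so symptoms may go unreported. The trial is also open-label, so tests ordered on suspicion need not be ordered equally often in the two arms.

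**Working it through.** The plan states no figure to reproduce. The first four steps compare sections, and the last two are arithmetic.

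**1. Named effect against the panel (protocol 13.1 and 12.2.2)**

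| Named effect | Scheduled measurement |
|---|---|
| Electrolyte disturbance | None: no sodium, potassium, chloride or other electrolyte |
| Osmolality disturbance | None directly; glucose and BUN are measured, but sodium is missing for a calculated value |
| Temporary renal failure | Creatinine and BUN, at two time points |

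Hematology has 6 items and chemistry 11, so 6 + 11 = 17 items. The number that are an electrolyte or osmolality is 0.

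**2. Timing.** The panel is drawn at Visit 1 and at Visit 14 (85d, or the early completion visit). Each subject therefore has one post-baseline sample at most.

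**3. SAP.** SAP section 8 and Tables 1001 to 1004 summarise the protocol panel. Tables 1003 and 1004 show ALP as the template and omit the remaining variables. No electrolyte or osmolality analysis is added anywhere.

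**4. Age of a reused baseline panel.** Screening runs from -14d to 0d, with consent at Visit 1, and the first application is on 1d. A result up to 14 days before consent is accepted. With consent at -14d, the oldest result dates from -14 - 14 = -28d. Its age at first application is 1 - (-28) = 29 days. Nothing requires such a panel to contain electrolytes.

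**5. What measurement would gain with 10 subjects in the Betafoam arm**

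- Exact (Clopper-Pearson) two-sided 95% upper limit with 0 events in n: 1 - 0.025^(1/n). For n = 10 this is 1 - 0.025^(1/10) = 0.3085, or 30.8%. The one-sided 95% limit is 1 - 0.05^(1/10) = 25.9%.
- Withdrawn subjects are not replaced. With 9 or 8 subjects sampled, the two-sided limit rises to 33.6% or 36.9%.
- Chance of at least one case among 10: 1 - (1 - p)^10. The documents give no event rate, so p is assumed:

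| Assumed true rate p | Chance of at least one case in 10 |
|---|---|
| 1% | 9.6% |
| 5% | 40.1% |
| 10% | 65.1% |
| 20% | 89.3% |

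These chances assume that all 10 are sampled and that the disturbance is present when the blood is drawn.

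**6. Volume of extra work.** 20 enrolled subjects x 2 samples = 40 samples at most. Each screening failure would add one Visit 1 sample.

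**The case against.** The strongest reply is that the plan already has a route for this risk. Unscheduled visits may include any laboratory test, abnormal findings and symptoms are adverse events, and the SAP tabulates non-local adverse events by arm (Tables 1101 to 1105 and 1112 to 1117). Section 13 describes precautions for marketed devices. It is not a list of safety endpoints, and nothing in the protocol promises an assay for every listed effect. In a purely exploratory pilot of 20 subjects, one more set of analytes settles little.

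Much of this stands, and it rules out several stronger readings:

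- A reader might infer that the trial has no means of detecting the effect at any visit. Protocol sections 12.1.5 and 17.1 do not support that. The gap concerns scheduled, systematic measurement, and so silent cases.
- A reader might infer that the laboratory tables are the only systemic safety data. The SAP also plans physical examination, vital signs and non-local adverse event tables.
- A reader might blame the missing tests for the trial's inability to exclude the risk. The sample size alone prevents that, as the 30.8% limit shows.
- A reader might take the scheduled 2 x 12 = 24 dressing applications as a minimum exposure. It is the count for a subject who stays the full 12 weeks; healed subjects finish early and others discontinue.
- A reader might think renal failure equally unmeasured. Creatinine and BUN are in the panel, though only at two time points.

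The reply does not remove the mismatch between sections 13.1 and 12.2.2. Tests done only when something prompts them do not give a balanced comparison between arms.

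**Conclusion.** The point holds in limited form. No scheduled laboratory item (0 of 17) measures the electrolyte or osmolality disturbance that section 13.1 names for Betafoam. Silent cases would not be detected systematically, and the arms could not be compared on this risk. Cases that cause symptoms, or come to light incidentally, can be recorded.

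This is an inexpensive improvement to safety description and does not undermine the trial. Its value depends on the true rate, which the documents do not give: over assumed rates of 1% to 20%, the chance of seeing at least one case among 10 runs from 9.6% to 89.3%. Even with the tests added, a disturbance that arises and resolves before the final sample would be missed.

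**What to change.** **Protocol.** In section 12.2.2 and in footnote 2 of the Schedule of study activities, add sodium, potassium and chloride to the chemistry at Visit 1 and Visit 14. Where a pre-consent panel is reused as baseline, require it to include these analytes; otherwise repeat it.

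**SAP.** Name the three analytes among the variables of Tables 1003 and 1004. Define calculated osmolality from sodium, glucose and BUN, giving the formula, units and reference range, and report it in the same tables. The assayed analytes fit the existing layout; only the derived variable needs a new definition.

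**Reporting.** Describe the result as detection and description, with the exact confidence interval, and not as evidence that the risk is absent.

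**Cost.** Three routine analytes on at most 40 samples from enrolled subjects, a few repeated baseline panels, and a wording change in both documents. No new visit is needed, and no new blood draw except where a reused panel lacks the analytes. An interim sample is not proposed: it would be an extra procedure, and interim visits may be replaced by home visits.

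If the sponsor prefers not to add the tests, the protocol and the report should state that this risk is followed only through adverse event reporting, so that the laboratory tables are not read as covering it.
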